6.3 Study Timeframe

The study will be initiated in January, 2018. Enrolment is expected to be completed by April 30, 2018.

Stage 2 analysis will not be part of the initial study read out, and will be performed at a later date.

6.4 Risks and Benefits to Subjects

GBCA observational study will only collect data for use of GBCAs including Clariscan as per clinical practice. No new procedure or intervention is recommended by the study protocol. There is no additional risk to the patients for taking part in the study. However, there is no direct benefit for the patient to take part in the study, but the understanding of the pattern of use, effectiveness and safety profile of GBCAs will improve the knowledge and understand of the MR procedures and will be beneficial for the society.

7 SELECTION AND WITHDRAWAL OF SUBJECTS

7.1 Procedures for Enrolment

After the start of the study all consecutive consenting adult and paediatric, male and female patients, undergoing MR procedures whose physician has made the decision to use GBCA as part of routine clinical practice will be enrolled. The enrolment of the total number of patients per centre will be limited to a defined number of patients for a centre (Table 1) with a maximum duration of recruitment of 3 months (month = 30days) from start date, i.e., first patient recruitment.

A subgroup of initial patients will be selected to transfer the anonymised images to GE Healthcare (GEHC) through AGMednet. The images will be archived at GEHC and analysed at a later date by an expert MR radiologist panel to assess the quality of images. The first 50 images will be transferred in a 1:1 ratio for Clariscan and other GBCAs, i.e., first consecutive 25 images (25 maximum or total recruited in 3 months) for Clariscan and other GBCAs. If sufficient number of images (25) for either group (Clariscan or other GBCAs) are not acquired in 3 months, the recruitment will stop at 3 months and all images will be transferred for the blinded read, the comparative analysis is not at centre level. All images will be pooled together for blinded image read by the expert panel.

7.2 Inclusion Criteria

7.2.1 Centre Criteria

A centre will be eligible for this observational study if all of the following apply:

- Centre included Clariscan on the formulary for MR examinations.
- Have electronic record of cumulative data and are willing to report the cumulative data at the end of the recruitment period.

7.2.2 Investigator Criteria

An investigator will be eligible for this observational study if all of the following apply:

- The MR radiologist is competent to perform and report MR examinations.
- Nurse/radiology technician and other members of his/her team are willing to participate in the relevant assessments outlined in this protocol.
- No other radiology team has been selected to take part in this study from this centre.

Where a radiology team has multiple physicians involved in the patients' diagnosis and contrast media selections, the radiology team should appoint a single overarching Principal Investigator of the Centre.

Alternatively the study can be focused on a specific patient group under the responsibility of a single physician, as most appropriate to the local circumstances.

7.2.3 Patient Criteria

A patient will be eligible for this observational study if all of the following apply:

- Male/Female patients of all age groups.
- Patients of all pathologies who require CE-MR imaging as part of their diagnostic work up and the radiologist/physician has made the decision to use extracellular GBCAs as part of routine clinical practice.
- Provided informed consent (directly or via a legal representative) to participate in the study

7.3 Exclusion Criteria

- Use of liver-specific GBCAs (Primovist and MultiHance when used for liver excretion properties).*

Note for exclusion criteria:

Please note if GBCAs are used off label in clinical practice for patients in indications not listed in the Summary of Product Characteristics (SPC), these will be reported as off label use.

*For liver-specific GBCAs used (where excretion by the hepatocytes is the mechanism as opposed to extracellular) no patient or procedure level data will be collected and these patients will also not be included in the subgroup of patients where image transfer will be done. There is no plan to do image assessment performed by liver-specific contrast medium as Clariscan does not have this indication and is not excreted by the liver. MultiHance, when used for liver excretion properties, will also not be included, but for all other indications it will be included for full data collection.

However, when reporting the overall number of MR procedures for the study centre and operating investigator, liver-specific agents will be reported in the cumulative data as the number of procedures done by liver-specific agents.

7.4 Withdrawal and Termination Criteria

7.4.1 Subject Withdrawal

There are no formal withdrawal criteria for this study. During the conduct of the study, the sponsor will review the safety data for trends and signals that would indicate the need for withdrawal of a subject.

In accordance with the Declaration of Helsinki, each subject is free to withdraw from the study at any time. Investigator(s) also have the right to withdraw subjects from the study in the event of illness, AEs, or other reasons concerning the health or well-being of the subject, or in the case of lack of co-operation.

Should a subject decide to withdraw after administration of the GBCA(s), or should the investigator(s) decide to withdraw the subject, all efforts will be made to complete and report the observations up to the time of withdrawal as thoroughly as possible. A complete final evaluation at the time of the subject's withdrawal should be made and an explanation given of why the subject is withdrawing or being withdrawn from the study.

The reason for withdrawal must be noted in the electronic Case Report Form (eCRF). If the reason for withdrawal is a clinical AE, monitoring will continue until the outcome is evident. The specific event or test result(s) must be recorded in the eCRF.

Subjects that withdraw will not be replaced.

7.4.2 Study or Site Termination

There are no formal termination criteria for this study. The sponsor reserves the right to terminate the study at any time.

8 IMAGING OF SUBJECTS

8.1 GBCAs Medicinal Product(s)

8.1.1 Clariscan 0.5 mmol/ml Solution for Injection

Clariscan 0.5 mmol/ml solution for injection will be administered as part of clinical practice according to the judgment of the site with regard to medical need. For more information, consult the SPC.

8.1.2 All GBCAs

Subjects will be administered a GBCA as part of clinical practice. All GBCAs will be selected by the sites and recorded as by the brand names.

8.1.3 Study Drug Accountability

No medicine will be provided by the Sponsor for the study. GBCAs will be used as part of clinical practice.

8.2 Method of Numbering Subjects and Assigning Subjects to Treatment Groups

Subject numbers will consist of 7 digits in total; the first 3 digits to identify the centre and the remaining 4 digits to identify the subject. Centre numbers will be in the format 001, 002, etc. Subject numbers for those who withdraw will not be reused.

Subjects will not be assigned to treatment groups because the choice of GBCA will be made by the investigator at the site as part of clinical practice.

8.3 Selection of Doses and Timing

Administration of Clariscan and MRI will be scheduled outside of this study as part of clinical practice; dosing and timing of imaging will have been selected at the discretion of the personnel at the imaging centre, also as part of clinical practice.

8.4 Blinding

This study is observational and no measures will be taken to try to blind participants.

8.5 Prior and Concurrent Therapy

Any medications taken by the subject within 24 hours of the MR examination through the end of the observation period will be recorded in the eCRF along with the indication. Either the generic or the trade name may be recorded.

8.6 Treatment Compliance

Not applicable to this study; all patients will be referred for a MR examination as part of clinical practice.

9 STUDY PROCEDURES

The MR examination will be performed as per routine clinical practice. The effectiveness and safety measurements obtained during the course of the study are summarised in the Study Schedule of Events ([Table 2](#)).

Table 2 Schedule of Assessments

Assessments	Enrolment Visit and Imaging Day 1	Day 7	Completion of Recruitment
Informed consent ¹	X		
Verify inclusion/exclusion criteria	X		
Enrolment and allocation of patient number	X		
Patient demographics, medical history, medication, and procedure information	X		
GBCA administration	X		
CE-MRI examination	X		
AEs/SAEs ²	X	X	
Quality of image assessment by local radiologist-Likert scale	X		
Diagnostic confidence by local radiologist ³	X		
Transfer of images	X	X	
Customer satisfaction by radiology technician/nurse			X
Investigator information - cumulative numbers for the recruitment period (date of the first patient to date of last patient at the centre) of the study at the centre			X
Centre information- cumulative numbers for the recruitment period (date of the first patient to date of last patient at the centre) of the study at the centre			X

AE = adverse event; SAE = serious adverse event

¹ Informed consent must be obtained before enrolment into the study.

² Adverse events (AEs) that occur in the first hour post-administration will be defined as “immediate”, and any AEs that occur >1 hour to 7 days post-administration will be defined as “delayed”.

³ Diagnostic confidence to be recorded by the local radiologist before the CE MR scan and again after the CE MR scan results are read.

9.1 Enrolment Visit and Imaging (Day 1)

All subjects must both satisfy the inclusion criterion and not satisfy the exclusion criterion listed in Sections [7.2](#) and [7.3](#). The following information will be collected from each subject prior to administration of GBCA:

- Informed consent
- Inclusion/exclusion criteria

- Demographic data
- Relevant medical history (a condition that is either active at enrolment or adversely impacts the subject's condition at enrolment; i.e., renal and hepatic status, history of allergy, rash urticaria, neurological problems, asthma, bronchoconstriction)
- Any medications taken by the subject within 24 hours of the MR examination through the end of the observation period will be recorded in the eCRF along with the indication
- Adverse events

Waivers or protocol exceptions will not be granted prospectively by the sponsor under any circumstances. Any exceptions to protocol specified requirements will be considered as protocol deviations.

After the subject is enrolled, the CE-MR procedure will be performed as routine clinical practice and findings reported in the eCRF. Information about the dynamic images or delayed enhancement images will be added:

- Quality of image assessment to be recorded by local radiology using a Likert scale
- Diagnostic confidence to be recorded by the local radiologist. Diagnostic confidence will be assessed first using only the non-enhanced image and then again using the contrast-enhanced image.
- AEs (immediate and delayed)

9.2 Post-Imaging Period

Safety measurements will be performed from GBCA administration until 7 days post-administration for AEs reported voluntarily by the patient. No follow-up safety assessment is required unless AEs are reported spontaneously by the patient or healthcare providers. However, AEs will be documented in line with the requirements applicable for use of medicines in general, irrespective of the documentation window.

The following information will be collected once at the end of the study:

- Customer satisfaction to be recorded by the local nurse/radiology technician once per centre for each GBCA used at the study centre, including generics
- Investigator information - cumulative numbers for the recruitment period (date of the first patient to date of last patient at the centre) of the study at the centre
- Centre information- cumulative numbers for the recruitment period (date of the first patient to date of last patient at the centre) of the study at the centre

The first 25 consecutive patients where Clariscan is used and the first 25 consecutive patients where any other GBCAs (all together 25 patients) is used, the images will be transferred for storage to allow a blinded image read by the expert MR radiology panel to be performed in a future analysis. If the recruitment is less than 25 for either group, then the total images done for the group (Clariscan or GBCAs) during the recruitment period will be transferred. If a patient has repeat imaging for technical reasons and the image is not readable and has been repeated for same indication/reason, then the second readable image will be transferred for storage and future analysis.

See Section 10.3 and the Study Schedule of Events Table ([Table 2](#)) for further details.

10 PATTERN OF USE, EFFECTIVENESS, SAFETY, AND OTHER VARIABLES

10.1 Pattern of GBCA Use

[figure not shown]
The pattern of use for GBCAs including Clariscan for MR (MR angiography [MRA]/MRI) examination will be assessed based on the following variables:

1. The number of radiological procedures, including ultrasound, MR, computed tomography (CT) scan, fluoroscopy, X-ray, single-photon emission CT (SPECT), and positron emission tomography (PET) examinations, performed by the study centre during the recruitment period of the study. The number of procedures done by the study centre will be collected once in the study and will be used to assess the percentage and proportion of different procedures performed by the radiology department, including the percentage of MR procedures with or without GBCAs (total GBCAs and individual GBCA).
2. Number of MR machines and staff (nurses and technicians) will be recorded to assess the workload per MRI machine and staff.
3. The number of radiological procedures, including ultrasound, MR, CT scan, fluoroscopy, X-ray, SPECT, and PET examinations, reported by the investigator during the recruitment period of the study. The number of procedures done by the centre will be used to assess the percentage and proportion of different procedures performed by the investigator (radiologist), including the percentage of MR procedures with or without GBCAs (total GBCAs and individual GBCA).
4. Use of GBCAs – Total and individual GBCA (generic GBCA recorded as a separate entity) use as per indication, organ/system imaged, age, gender, body mass index (BMI; <18 is “underweight”, 18 to 25 is “normal”, 26 to 30 is “overweight”, 30 to 40 is “obese”, and >40 is “morbidly obese”), reason for use of GBCA and preference for a particular GBCA due to BMI.
5. Referral pattern for CE-MRI - Following information will be assessed:
 - a. Referring physician
 1. seniority (house officer or equivalent, registrar, consultant, super specialist)
 2. specialty (e.g., cardiologist oncologist)
 - b. The quality of referral will be assessed by the radiologist as follows:
 - 1 = not enough information
 - 2 = have all necessary information

3 = good full detailed information with clear question

6. Repeat MR examinations done will be reported with the reason for repeat examination. Repeat examination will be defined as an MR examination for the same indication/reason as for the first examination, not follow-up MR or MR examination to answer a different question. In addition, assessment will be made for individual GBCA.
7. Assessment of the referral note recorded verbatim in the open text section will be assessed qualitatively for emerging themes and patterns.
8. Challenges for radiology department will be assessed qualitatively for emerging patterns and themes.

Figure 2 Pattern of Use

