10.4 Other Variables

10.4.1 Demographic Data

Subject date of birth, gender, height, weight, and BMI (calculated) will be collected.

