10.4.2 Medical and Surgical History

- Medical history (including, in particular, history of allergy/asthma, eczema, renal, neurological)
- Number of previous MR, SPECT, PET, special x-ray examinations (e.g., fluoroscopy, barium studies) and CT examination for current illness/disease
- Major comorbidity and renal (level of renal impairment if know)/hepatic status
 - Renal impairment will be recorded as:

Every effort will be made to understand the stage of renal impairment based on estimated glomerular filtration rate (eGFR). The stages of chronic kidney disease (CKD) are classified as follows:

1. Stage 1: Kidney damage with normal or increased glomerular filtration rate (GFR; >90 mL/min/1.73 m²)
2. Stage 2: Mild reduction in GFR (60 to 89 mL/min/1.73 m²)

3. Stage 3a: Moderate reduction in GFR (45 to 59 mL/min/1.73 m²)
4. Stage 3b: Moderate reduction in GFR (30 to 44 mL/min/1.73 m²)
5. Stage 4: Severe reduction in GFR (15 to 29 mL/min/1.73 m²)
6. Stage 5: Kidney failure (GFR <15 mL/min/1.73 m² or dialysis)

Information regarding renal replacement therapy should be noted.

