12.5.3 Patient-Level Variables

The following summaries will be provided for the Full Analysis Set:

- The number of times a GBCA was used per indication, organ/system imaged, age, gender, BMI, reason for use of GBCA and preference for a particular GBCA based on BMI.
- The number of each type of referring physician (seniority or specialty).
- The quality of the referral during the recruitment period of the study.

- The number of repeat MR examinations that are performed during the recruitment period of the study and a summary of the reasons for repeat exams.

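### The BMI classes place a BMI of 30 in two classes, leave unrounded values between 25 and 26 in none, and apply one set of cut-offs to adults and children alike

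*Protocol*

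**What the plan says.** Protocol section 10.1, item 4 lists total and individual GBCA use by several factors, BMI among them, and fixes five BMI classes. The lower two are "<18 is “underweight”, 18 to 25 is “normal"; the upper three are "26 to 30 is “overweight”, 30 to 40 is “obese”, and >40 is “morbidly obese". The three middle classes, where the boundaries matter here, read in sequence "18 to 25 is “normal”, 26 to 30 is “overweight”, 30 to 40 is “obese". The synopsis gives the same cut-offs.

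Section 10.4.1 shows where BMI comes from: "Subject date of birth, gender, height, weight, and BMI (calculated) will be collected". I found no rounding rule in the protocol.

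Enrolment has no age limit. Section 7.2.3 admits "Male/Female patients of all age groups", and section 7.1 enrols "all consecutive consenting adult and paediatric, male and female patients". There is no paediatric version of the classes and no age restriction on them.

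The breakdown is a planned Full Analysis Set summary in section 12.5.3: "The number of times a GBCA was used per indication, organ/system imaged, age, gender, BMI", among other factors. Pattern of use is the primary objective (section 5.1). Section 12.3 separately summarises BMI with descriptive statistics.

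Section 10.4.2 has a similar list for renal function. Stage 1, "Kidney damage with normal or increased glomerular filtration rate", is set at above 90 mL/min/1.73 m², and Stage 2 at 60 to 89.

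**The concern.** A set of classes used for counting should put every patient in exactly one class. These do not, and the gap and the overlap sit in the middle of the scale, where many adult patients can be expected. With the classes as written, whoever programs the table must decide where these patients go, possibly after seeing the data. Two programmers could produce different tables from the same protocol.

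The age problem is separate. BMI in children depends on age, so one unindexed set of cut-offs can label a child underweight because of age alone. The underweight row would then partly describe GBCA use in children, which confounds the BMI breakdown with the age breakdown.

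What is at stake is the correctness of the BMI-class tables, one component of the primary pattern-of-use description. No hypothesis test depends on them.

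**Working it through.** The protocol gives no figure to reproduce here. The check is whether the classes partition the BMI scale, and how many patients could be affected if they do not.

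**Step 1: code the classes as written** (section 10.1, item 4), treating each range as including both end values.

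| BMI | Class or classes |
|---|---|
| 17.9 | underweight |
| 18 | normal |
| 25 | normal |
| 25.5 | none |
| 26 | overweight |
| 30 | overweight and obese |
| 40 | obese |
| 40.1 | morbidly obese |

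All values from 10 to 60 in steps of 0.1 were tested: 25.1 to 25.9 have no class, and 30.0 has two. The boundaries at 18 and 40 are clean. With whole numbers from 10 to 60, no value is unclassified, but 30 still has two classes.

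**Step 2: examples.** 74 kg at 1.70 m gives 74/1.70² = 25.6, which has no class. A child of 18 kg and 1.10 m gives 18/1.10² = 14.9, labelled underweight whatever the child's age.

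**Step 3: size.** This is an assumption, because the protocol gives no BMI distribution. Take BMI as normal with mean m of 25 to 27 and SD s of 4.5 to 5.5.

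- Unclassified if unrounded: Φ((26 − m)/s) − Φ((25 − m)/s)
- Double-classified if rounded to whole numbers: Φ((30.5 − m)/s) − Φ((29.5 − m)/s)
- Double-classified if rounded to one decimal: Φ((30.05 − m)/s) − Φ((29.95 − m)/s)

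For m = 26, s = 5, the unrounded gap is Φ(0) − Φ(−0.2) = 0.500 − 0.421 = 7.9%. The tie at 30 with whole numbers is Φ(0.9) − Φ(0.7) = 0.816 − 0.758 = 5.8%.

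| m, s | Between 25 and 26, unrounded | At 30, whole numbers | At 30, one decimal |
|---|---|---|---|
| 25, 4.5 | 8.8% | 4.8% | 0.5% |
| 26, 5 | 7.9% | 5.8% | 0.6% |
| 27, 4.5 | 8.4% | 7.1% | 0.7% |
| 27, 5 | 7.6% | 6.7% | 0.7% |
| 27, 5.5 | 7.0% | 6.2% | 0.6% |

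The Table 1 allocations sum to 200 + 900 + 1,200 + 1,000 + 300 + 250 + 900 = 4,750; the stated ceiling is 5,400. Both are maxima. The unrounded gap of 7.0% to 8.8% is about 330 to 420 of 4,750, or about 380 to 475 of 5,400. A wider assumption (mean 24 to 28, SD 4 to 6) gives about 6% to 10%, or about 330 to 530 of 5,400.

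**Step 4: the eGFR list** (section 10.4.2). In whole numbers, only exactly 90 has no stage. If eGFR is recorded with decimals, values between 89 and 90, 59 and 60, 44 and 45, and 29 and 30 also have none.

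**The case against.** The strongest reply is that the protocol writes its ranges in whole numbers, as the renal list shows with 60 to 89, 45 to 59 and so on. On that reading nothing lies between 25 and 26, and a rounding rule is the kind of detail an SAP usually supplies. This stands as far as the gap goes: the gap holds only for BMI that is not rounded to whole numbers. It does not rescue the classes. The value 30 is in two classes on any reading, and whole-number rounding widens that overlap to everyone from 29.5 to 30.5.

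The limits on consequence also stand. BMI is one of several factors in item 4, itself one of eight pattern-of-use items. Height, weight and BMI are all recorded, BMI is summarised continuously under section 12.3, and the study tests no formal hypothesis.

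A reader might infer more than the documents support:

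- **Unclassified patients are lost from the analysis.** Nothing says so. Section 12.10 keeps data from all dosed subjects in summaries where appropriate.
- **The item on preferring a GBCA because of BMI is also corrupted.** It is listed separately, and nothing shows that it is derived from the classes.
- **The 7-9% is a property of this study.** It rests on an assumed, adult-like BMI distribution.
- **A known share of children is mislabelled.** The protocol gives no paediatric share, and does not itself call the cut-offs adult ones; that is general knowledge. The text does establish that one set applies at every age.

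**Conclusion.** The point holds for the BMI-class tables. As written, the classes are not mutually exclusive on any reading and, for unrounded BMI, not exhaustive. Under the assumed normal distribution (mean 25-27, SD 4.5-5.5), about 7-9% of patients would be unclassified if BMI is unrounded, or about 5-7% would be in two classes if it is rounded to whole numbers. At one decimal the overlap alone is only about 0.5-0.7%, but the gap then remains. The mixing of children with low-weight adults in the underweight row follows from all-age enrolment; its size cannot be stated from the protocol.

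The rest of the primary pattern-of-use description is unaffected. This is a definition error that should be corrected before the tables are programmed. An SAP that is not shown might restate the classes, but it would then depart from cut-offs that the protocol fixes in two places, and section 12.12 requires departures from the protocol's analysis to be reported. The eGFR list is a minor secondary instance.

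**What to change.** In the synopsis and section 10.1, item 4, define contiguous, non-overlapping classes on unrounded BMI, for example <18, 18 to <25, 25 to <30, 30 to 40, >40. This keeps the existing clean boundaries at 18 and 40. It moves a BMI of exactly 25 from normal to overweight; another convention would serve equally well, provided each boundary value falls in one class only.

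State that the classes apply to adults, give the age threshold, and summarise BMI or weight of younger patients separately by age group.

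As a minor companion change, make all the eGFR recording categories in section 10.4.2 contiguous, including the value of exactly 90. Repairing only the boundary between Stages 1 and 2 would leave the other gaps open for values with decimals.

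The cost is wording and one derivation rule. Date of birth, height and weight are already collected, so data collection does not change.
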